**b) Inclusion and Exclusion Criteria**

Inclusion Criteria:

1. Documented TBI of any severity
2. At least 12 months post injury (PTBIF typically stabilizes by 12 months)
3. Presence of clinically significant fatigue, operationalized as a score of 22 or more on the Multidimensional Assessment of Fatigue (an empirically based cut point previously used for clinical fatigue in TBI);

	Protocol Name:	Management of post-TBI fatigue with light exposure
	Principal Investigator:	[name]., ABPP/Cn
	Primary Contact Name/Contact Info:	[name], [contact] , [name]
	Date Revised:	3/9/2016
	Study Number:	IF1813452

4. Age 18 or older
5. English speaking

Exclusion Criteria:

1. Neurological disease other than TBI
2. Pregnancy (because of pregnancy fatigue)
3. Medical illness causing fatigue, such as anemia, hypothyroidism, HIV, renal failure, cirrhosis or cancer treatment in the past year
4. Current major depressive episode or substance abuse
5. Diagnosed sleep disorder or high risk for sleep apnea
6. History of bipolar disorder or manic or hypomanic episodes
7. Current chronic, severe headaches
8. Sensitivity to bright light
9. History of retinal damage or disease.

**6) (NOTE: You may not include members of vulnerable populations as subjects in your research unless you indicate this in your inclusion criteria.)**

**a) Number of Subjects**

To obtain the necessary sample size of 80 study completers with 40 in each treatment arm, we conservatively estimate that we will need to screen 136 individuals (30% negative screens) and enroll 95 of them (15% attrition).

**b) Study Timelines**

Subjects' participation in the study will last approximately two months. Assessments will be conducted at three points: T1 (baseline), T2 (end-of-treatment) and T3 (follow-up at one month post treatment). Actigraph data will be collected for 3 days at T1 (prior to the initiation of treatment). Participants will use the light box for 4 weeks and then return at T2 for repeat administration of the measures and Actigraphy for 3 more days. T3 will take place 4 weeks after light box treatment is completed and will not involve the Actigraph.

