We have also conducted an *Intervention Development* study to examine the feasibility and safety of BWL treatment in individuals with PTBIF, to estimate effect size and assess sensitivity of measures. We randomized 13 individuals with PTBIF to receive 28 days of treatment with BWL or DRL. DRL is widely used as a placebo in light therapy studies because it is relatively inactive biologically, and is known to induce positive treatment expectations comparable to those of BWL, even though it is visibly different from BWL. Treatment involved sitting in front of the light box for 30 minutes per day within 30 minutes of waking. Actigraphy data and sleep diaries were collected for 3 days before and after treatment. Participants completed measures of fatigue, sleepiness, sleep quality, mood, treatment satisfaction, treatment credibility and outcome expectancy, before and directly after treatment and again one month after treatment.

	Protocol Name:	Management of post-TBI fatigue with light exposure
	Principal Investigator:	[name]., ABPP/Cn
	Primary Contact Name/Contact Info:	[name], [contact] , [name]
	Date Revised:	3/9/2016
	Study Number:	IF1813452

*Safety, feasibility and treatment compliance.* Side effects and adverse events were monitored weekly for all participants: none were reported in either treatment condition. All participants were able to use the light box independently at home. Some requested additional telephone guidance on the use and positioning of the light box; 8 of 12 reported “no difficulty” using the box and 4 experienced minor initial difficulties (e.g., angling it correctly). Daily reminders helped participants remember to complete their sleep diaries. Ten participants reported missing no treatment sessions; the other 2 reported missing 2 and 4 sessions each. One subject dropped out after one week of treatment saying that light box use conflicted with her schedule.

*Treatment credibility and satisfaction.* Treatment credibility measures were administered 1-2 weeks after starting treatment. Both treatments were found to be credible and subjects in both groups reported that they expected substantial symptom improvement. Satisfaction with treatment outcome was somewhat better in the BWL group.

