*Treatment effects.* Change scores were used for between-group comparisons to remove effects of any baseline differences between groups. Robust effect sizes in Cohen’s “medium” and “large” ranges were seen for BWL both between and within groups (0.32-1.56) on fatigue measures (see Appendix VI for all effect sizes). In most cases, effects were somewhat decreased at follow up but were generally in the medium range. This is unexpected, as past research indicates that treatment effects dissipate after treatment is discontinued. Medium or larger effect sizes were also noted for BWL on measures of daytime sleepiness, sleep quality and mood. Effect sizes for DRL were generally small.

Actigraphy findings indicated improvements in sleep in both groups but with larger effect sizes for BWL. Circadian rhythm data were more ambiguous, with modest changes in phase and rhythmicity in both groups. These findings suggest that BWL and DRL therapy are safe, feasible and credible for use with individuals with TBI, that the measures selected were sensitive to treatment effects and that BWL may be a promising treatment for PTBIF, with potential benefits for daytime sleepiness, mood, circadian rhythms and sleep as well. Indeed, daytime sleepiness, mood, circadian rhythms, and sleep quality may actually function as mediators or moderators of BWL treatment effects on PTBIF, given their documented responsiveness to light exposure. Because of the promising initial findings in our small pilot study and the need for empirically validated PTBIF treatment, an *Intervention Efficacy* trial investigating the effect of BWL on PTBIF is warranted. Based on: 1] the literature on alerting effects and cognitive benefits of BWL and the connection between PTBIF and cognition; 2] our own unpublished research suggesting the important role of anxiety in PTBIF and sleep disturbance; and 3] potential improvements in life satisfaction resulting from BWL effects on function, we will evaluate cognition, anxiety and life satisfaction as potential secondary effects of treatment.

To date, no trials of BWL treatment have been conducted in individuals with TBI. However,

	Protocol Name:	Management of post-TBI fatigue with light exposure
	Principal Investigator:	[name]., ABPP/Cn
	Primary Contact Name/Contact Info:	[name], [contact] , [name]
	Date Revised:	3/9/2016
	Study Number:	IF1813452

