After one month of light treatment (T2), we will re-administer the baseline battery along with satisfaction and user experience questionnaires and 3 more days of Actigraphy. One month after T2, we will administer the assessment battery a third and final time (T3). Research team members who conduct outcome assessments will be blind to participants' treatment allocations. They will enter the data only after the participants have completed all study assessments (i.e. after T3) to avoid bias. Participants will be asked not to reveal treatment allocation to research team members. Participants will also be asked to refrain from light treatment in the month intervening between T2 and T3. Upon completion of follow-up, interested participants will be offered a discount coupon to purchase their own light box if they wish to do so.

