*RQ1: We will assess whether treatment with BWL is associated with changes in circadian rhythms and improvements in anxiety, cognition and life satisfaction using the analyses described for H1, with Neuro-QOL Anxiety, CNS Vital Signs Neurocognitive Index and CFQ (cognition), and SWLS (life satisfaction) as the respective dependent variables.*

*RQ2: As it is not clear whether BWL's effects on PTBIF are direct effects or secondary to changes in other domains, we will examine whether PTBIF scores are mediated or moderated by mood, sleepiness, sleep quality and circadian rhythms. These analyses will focus on the magnitude of the effect, as recommended by Kraemer et al. We will use a fixed-effects approach in which the dependent variable is the GFI pre-post change. We will compare the between treatment group effect sizes for those with and without the respective potential mediator or moderator. An effect will be considered present if a substantial difference in effect size is observed. Results from these exploratory analyses could be used to guide the design of future RCTs that would focus on those subjects most likely to respond to BWL.*

*RQ3: Because current research suggests that age, gender and injury severity may be associated with treatment outcome, we will examine these individual characteristics and any others that the literature suggests may be relevant at the time of analysis. We will add these variables to the multilevel model one at a time and test to determine if the variable improves fit. Continuous variables that improve the fit will be examined further by determining the correlation between them and GFI separately for the two treatment groups, and comparing the strength of the correlations.*

e. Statistical Power

[The sample size for this study will provide adequate power to test the primary hypothesis. We will recruit enough subjects to fill the Treatment (DRL-BWL)-by-Time (pre-post) repeated measures design (40 subjects per treatment group, total N = 80). This design achieves 90% power to test the treatment effect using a Geisser-Greenhouse Corrected F Test with a 5% significance level, based on an effect size of 0.37, and achieves 81% power to test the Treatment-by-Time interaction using a Geisser-Greenhouse

	Protocol Name:	Management of post-TBI fatigue with light exposure
	Principal Investigator:	[name]., ABPP/Cn

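### The second Actigraph recording begins after light treatment has ended, so the circadian outcome describes the first days off light and, for RQ2, follows the T2 GFI it is meant to explain

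*Combined protocol and SAP*

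**What the plan says.** Study Timelines (repeated in the overview under Procedures) says that participants are to "use the light box for 4 weeks and then return at T2 for repeat administration of the measures and Actigraphy for 3 more days". Enrollment and Assessments places the T2 battery in the same order: "After one month of light treatment (T2), we will re-administer the baseline battery along with satisfaction and user experience questionnaires and 3 more days of" wrist-device recording. The same section adds: "Participants will also be asked to refrain from light treatment in the month intervening between T2 and T3". On follow-up, Study Timelines says: "T3 will take place 4 weeks after light box treatment is completed and will not involve the Actigraph".

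Study Timelines labels T2 as the end-of-treatment assessment. The circadian hypothesis (H3 under Objectives, H2 in the analysis plan) concerns people receiving 4 weeks of daily BWL. Its circadian dependent variables come from actigraphy, whereas sleep quality is measured by NeuroQol Sleep. Data Processing also lists sleep statistics derived from the Actigraph, but no hypothesis or research question names them as a dependent variable.

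For mechanism, RQ2 says that "we will examine whether PTBIF scores are mediated or moderated by mood, sleepiness, sleep quality and circadian rhythms", with the pre-post change in GFI as the outcome. In the Background, the pilot followed the same pattern: "Actigraphy data and sleep diaries were collected for 3 days before and after treatment".

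**The concern.** A recording that starts once treatment has stopped measures the early post-treatment state. The hypothesis is about the state under daily light. If the circadian effect fades quickly, a null result could mean either that light did nothing to rhythms or that the effect had begun to fade. No other recording in the trial could separate the two.

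The second issue is time order. A mediator should be measured before the outcome it is said to transmit. Here the T2 GFI is collected at the visit and the circadian data over the following three days, so a circadian mediation result could not be read as mediation. Aim 3 is about mechanism, which makes this more than a matter of labels.

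**Working it through.** **1. When light ends relative to T2.** Three statements bear on this.
- Light is used for 4 weeks and the T2 visit comes next (Study Timelines).
- Participants refrain from light from T2 to T3 (Enrollment and Assessments).
- T3 is 4 weeks after light ends (Study Timelines) and also one month after T2 (Enrollment and Assessments), which puts T2 at about the end of light. The protocol uses 4 weeks and one month interchangeably, so this agreement is good only to about 2 or 3 days (30 − 28 or 31 − 28). It supports the other two statements but would not settle the point alone.

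No statement continues light through the T2 recording or places any recording during light use.

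**2. Nights off light.** The documents do not say whether the last session is on the T2 day or the day before.
- Visit on the last light day, after the morning session: the three nights follow 0, 1 and 2 mornings without light.
- Visit on the next day: they follow 1, 2 and 3.

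So two or three of three nights are off light. On either count, no light session falls inside the recording.

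**3. Which outcomes are touched.**
- Circadian measures (secondary outcome): from the Actigraph, affected.
- Actigraphic sleep statistics: affected, but not a named dependent variable.
- NeuroQol Sleep, ESS and Neuro-QOL Depression: not taken from the Actigraph, so not affected.
- GFI (primary): not affected.

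**4. Order of measurement for RQ2.** The circadian change uses the recordings made after the T1 battery and after the T2 battery. The GFI change uses the T1 and T2 batteries. The post-treatment circadian value therefore follows the post-treatment GFI. As a moderator, circadian rhythm can use the T1 recording, which precedes treatment. Mood, sleepiness and sleep quality are measured at the same visit as GFI.

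**5. The plan's power figures, then an illustration.** Read the effect sizes in Statistical Power as Cohen's f. With two time points the Geisser-Greenhouse correction has no effect. Power comes from a noncentral F with 1 and N − 2 = 78 degrees of freedom, λ = N·f², two-sided 5%, N = 80.
- f = 0.37: λ = 80 × 0.1369 = 10.95, power 90.5% (stated 90%).
- f = 0.32: λ = 80 × 0.1024 = 8.19, power 80.7% (stated 81%).

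Both reproduce. They belong to the primary hypothesis; the documents give no circadian effect size and no rate of loss. Purely as an assumption, let the on-light circadian effect be f = 0.32 (standardised difference 2f = 0.64):

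| Effect lost by the recording | f | λ | Power |
|---|---|---|---|
| 0% | 0.320 | 8.19 | 81% |
| 10% | 0.288 | 6.64 | 72% |
| 25% | 0.240 | 4.61 | 56% |
| 50% | 0.160 | 2.05 | 29% |

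The table shows how sensitive power would be to a loss. It is not evidence that a loss occurs.

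**The case against.** The strongest reply is that nothing shows an effect is lost. The Background does say that "past research indicates that treatment effects dissipate after treatment is discontinued", but it says so to explain why the pilot result was unexpected: pilot effects at one-month follow-up were generally still medium. The analysis plan repeats that pilot data suggest persistence. Pilot actigraphy was also taken after treatment, and sleep improvements were still larger with BWL. This stands in part. A reader might infer that a real circadian effect is diluted, or that power falls from 81% to 29%. The documents support neither, because the size of any loss over three days is not given. The pilot does not remove the doubt either: its circadian findings were ambiguous and came from the same kind of post-treatment window.

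A reader might also infer that the sleep-quality outcome is off treatment, or that all three nights certainly are. The first is wrong, since that outcome is a questionnaire. The second depends on the day of the last session, which is not stated.

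It can be argued that T2 is a window, so that the instruction to refrain between T2 and T3 does not strictly cover the three recording days. The wording that participants finish 4 weeks and then return makes this the weaker reading.

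On mediation, RQ2 is exploratory and compares effect sizes, and the other candidate mediators do not precede GFI either. A recording a few days earlier would still be a single post-baseline measure. That is fair: the right order is necessary for mediation, not sufficient. It does not justify a measure that comes after the outcome.

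Finally, recording off light at both T1 and T2 keeps conditions matched. That advantage is real but small, because the added seated time under light would be the same in both arms.

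**Conclusion.** The point holds for the circadian outcome and for circadian mediation in RQ2. As written, the trial collects no on-light actigraphy, and analysis cannot recover it. What is called an end-of-treatment circadian result is an early post-treatment one, with two or three of three nights off light. The post-treatment circadian measure follows the T2 GFI, so it can show association but not mediation.

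The reach is limited to one secondary outcome domain, the unassigned actigraphic sleep statistics, and one exploratory question. The between-arm comparison is not confounded, moderation by baseline rhythm is intact, and the primary test is untouched. Loss of circadian effect is possible but not shown, and the power range above rests on an assumed effect and assumed losses. The conclusion assumes the plain reading that light use stops by the T2 visit. The change is worth making because it is cheap, but it is not critical to the trial's main result.

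**What to change.** Leave the light schedule as it is. Move the second 72-hour Actigraph recording, with a sleep diary as at T1, to the last three days of light use. For example, send the device in week 4 and collect it at T2. Use this recording for the circadian outcome, the actigraphic sleep statistics and RQ2, and state the recording days relative to the last light session.

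If a post-light recording is kept, alone or in addition, call it a measure of early post-treatment persistence. If it is the only one, report the RQ2 circadian result as association, not mediation.

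The cost is protocol wording and getting the device to participants before T2 instead of recovering it afterwards. Wear time for a single recording, sample size and the primary analysis do not change. There are two small downsides. The T2 recording would contain 30 seated minutes a day that the T1 recording lacks, equally in both arms. And if the device records light, the light channel must be hidden from whoever marks the night intervals, since it could reveal allocation.

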**c) Endpoints**

The primary study outcome will be fatigue. Secondary outcomes will include sleepiness, circadian rhythms, mood, satisfaction with life, cognition, anxiety and sleep quality.

**d) Procedures Involved in the Human Research**

Overview of Treatment/Assessments

Subjects' participation in the study will last approximately two months. Assessments will be conducted at three points: T1 (baseline), T2 (end-of-treatment) and T3 (follow-up at one month

	Protocol Name:	Management of post-TBI fatigue with light exposure
	Principal Investigator:	[name]., ABPP/Cn
	Primary Contact Name/Contact Info:	[name], [contact] , [name]
	Date Revised:	3/9/2016
	Study Number:	IF1813452

post treatment). Actigraph data will be collected for 3 days at T1 (prior to the initiation of treatment). Participants will use the light box for 4 weeks and then return at T2 for repeat administration of the measures and Actigraphy for 3 more days. T3 will take place 4 weeks after light box treatment is completed and will not involve the Actigraph. Subjects will be paid \$20 for completion of each study assessment (including \$10 for a screening assessment prior to T1).

### Enrollment and Assessments

Potential participants who contact the research team and express interest in the study will undergo the informed consent procedure followed by a screening assessment to assess eligibility. We will obtain consent in accordance with federal and MSSM regulations. Participants who qualify for the study will complete the remaining items from the T1 battery at this point. To document the presence of TBI, they will be asked to provide detailed information about their injury (mechanism, date, severity) and provide medical records or sign releases allowing us to access medical records documenting their TBI.

After completing the baseline battery, we will give participants an Actigraph. They will wear the Actigraph for 72 hours before starting the intervention. They will also complete a sleep diary on which they will record time to bed and time awake. After these three days, they will return to the research center, and we will download their Actigraph data. We will then train participants to use the light box. Consistent with American Academy of Neurology criteria for intervention studies we will then randomly assign subjects to receive either BWL or DRL using a predetermined, random sequence in blocks of randomly determined size between 6 and 10. A staff member of the BIRC who has no contact with the study participants and is not otherwise involved in the project will do the randomization. He or she will provide the research assistant with a case containing the appropriate light box (note that the BWL and DRL light boxes are indistinguishable). Participants will be asked to record their use of the light boxes and their fatigue on a daily basis. A week after treatment begins participants will be called and asked to complete an assessment of treatment credibility and outcome expectancy.

After one month of light treatment (T2), we will re-administer the baseline battery along with satisfaction and user experience questionnaires and 3 more days of Actigraphy. One month after T2, we will administer the assessment battery a third and final time (T3). Research team members who conduct outcome assessments will be blind to participants' treatment allocations. They will enter the data only after the participants have completed all study assessments (i.e. after T3) to avoid bias. Participants will be asked not to reveal treatment allocation to research team members. Participants will also be asked to refrain from light treatment in the month intervening between T2 and T3. Upon completion of follow-up, interested participants will be offered a discount coupon to purchase their own light box if they wish to do so.

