**5) Study Design**

**a) Recruitment Methods**

We will use recruitment techniques that have proved successful in our research, including flyers and discussions with our patients with PTBIF. We will distribute recruitment materials to individuals who participate in other studies or who attend support groups at our center, at consumer conferences and to previous research participants who have expressed willingness to be contacted for future studies. We will post information about the study on the MSMC and Mount Sinai Brain Injury Research Center websites and Facebook page, on Brain Injury Association websites and on clinicaltrials.gov. We will also contact patients seen by our collaborating physiatrists using post mail. Additionally we will distribute recruitment materials at other medical centers serving patients with TBI, such as NYU Langone Medical Center, through collaborating psychologists with patients appropriate for research. Our prior recruitment experience suggests that the sample will be diverse in terms of demographics and injury-based characteristics.

Additionally, we have added the Centre for Neuro Skills facilities, post-acute rehabilitation centers in Bakersfield, CA, Los Angeles, CA, and Dallas, TX as external sites for this project. The site expects to add 30-40 participants per year to the protocol. Patients undergoing post-acute rehabilitation at the Centre for Neuro Skills will be approached for participation in the study.

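### Randomisation is described as one blocked sequence without site strata and the models name no site term, although three added rehabilitation centres may supply a large share of the sample; a cheap improvement.

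*Combined protocol and SAP*

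**What the plan says.** **Allocation.** Under Enrollment and Assessments, participants are assigned "using a predetermined, random sequence in blocks of randomly determined size between 6 and 10". The task is central: "A staff member of the BIRC who has no contact with the study participants and is not otherwise involved in the project will do the" randomisation. No stratification factor is named there or elsewhere.

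**Sites.** Recruitment Methods adds "post-acute rehabilitation centers in Bakersfield, CA, Los Angeles, CA, and Dallas, TX as external sites for this project". It states "The site expects to add 30-40 participants per year to the protocol" and "Patients undergoing post-acute rehabilitation at the Centre for Neuro Skills will be approached for participation in the study". The main centre recruits by other routes: flyers, websites, mailings to collaborating physiatrists' patients, and "individuals who participate in other studies or who attend support groups at our center". All sites share the eligibility criteria, including "At least 12 months post injury". The target is "80 study completers with 40 in each treatment arm", from 95 enrolled.

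**Analysis.** Sections 6.b and 6.c of the statistical plan build the model from time, then covariates chosen from preliminary analyses, then treatment. The random effects are justified by repeated measurement within a person. A covariate enters if a baseline imbalance on a demographic or clinical variable is significant, or if preliminary analyses flag it as a potential confounder. The research question on individual characteristics names age, gender and injury severity. Site is not mentioned.

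**The concern.** The allocation and the models read as if written for one centre, while the trial now has four locations and two recruitment streams. A single blocked sequence balances the arms overall but not within a site. Participants in active rehabilitation could plausibly follow a different fatigue course over four weeks from community volunteers. If so, a chance excess of one stream in one arm moves the treatment contrast, and variation between sites stays in the error term. With no pre-specified site term, any later adjustment would be a data-driven choice.

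**Working it through.** **1. The plan's own power.** Inputs from section 6.e: N = 80, alpha 0.05, effect sizes 0.37 (treatment) and 0.32 (treatment-by-time). Read as Cohen's f, with a noncentral F on 1 and 78 df and noncentrality N·f²:
- f = 0.37: noncentrality 80 × 0.1369 = 10.95, power 90.5% (stated 90%).
- f = 0.32: noncentrality 80 × 0.1024 = 8.19, power 80.7% (stated 81%).

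Both reproduce. On the change scale, f = 0.32 is d = 2 × 0.32 = 0.64.

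**2. Share from the added centres.** Annual accrual × years / 95, reading 30-40 as the total for all three centres and as part of the 95:

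| Years (assumed) | Participants | Share of 95 |
|---|---|---|
| 0.5 | 15-20 | 16-21% |
| 1 | 30-40 | 32-42% |
| 2 | 60-80 | 63-84% |

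If they come on top of the 95, the share is 24-30% after one year (30/125 to 40/135) and 39-46% after two (60/155 to 80/175).

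**3. Chance imbalance.** Take 95 randomised, 47 and 48 per arm, 40 from the added centres, all sites recruiting throughout. The hypergeometric SD of the count in one arm is 2.42. The SD of the difference in site share is 2.42 × (1/47 + 1/48) = 0.102. The chance of a difference of 15 points or more is 14.7%, and of 20 points or more 6.2%. Simulating blocks of 6, 8 or 10 gives nearly the same, so overall blocking hardly helps within site. The timing of entry matters:

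| Places left when added centres start (assumed) | 15 points or more | 20 points or more |
|---|---|---|
| 95 | 15% | 6% |
| 60 | 6% | 2% |
| 45 | 0.3% | under 0.1% |

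**4. What an imbalance does.** The shift in the estimate is the imbalance times the site difference in change. At 20 points and 0.5 SD (assumption) it is 0.20 × 0.5 = 0.10 SD. The standard error with 95 participants is √(1/47 + 1/48) = 0.205 SD, so this is about half a standard error.

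**5. Validity and power.** Simulation with N = 80, d = 0.64 and 42% or 63% of participants from the added centres:
- No strata and no site term: type I error 0.047-0.053, mean estimate unbiased.
- Sites differing by 0.5 SD in change: power 77-79% without strata or site term, against 80-81% with both.
- At 0.8 SD: about 75% against 81%.
- Strata but no site term: type I error drifts down to about 0.04 when sites differ, and power is 76-79%. Stratifying therefore needs the model term as well.

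**6. Which model term acts.** With two time points and complete data, the treatment-by-time estimate is the between-arm difference in mean change. A site main effect adds the same constant to a person's two values and cancels in the change. Fitting a random-intercept model to simulated data confirms it: the treatment-by-time estimate and its standard error were identical with and without a site main effect, and changed only when site-by-time was added.

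**7. Cost in power.** Even three site terms on the change scale (75 error df) leave interaction power at 80.7% if site explains nothing. If site explains 5%, 10% or 20% of the variance in change, power is 82.6%, 84.6% or 88.5%.

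**The case against.** A reader might infer that the result would be confounded by site, or that the type I error is inflated. Neither follows: allocation is random, and the simulated error rate stays near 5%.

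A reader might also take a 0.5-1.0 SD site difference in fatigue level as the measure of harm. Stable level differences cancel in pre-post change; only differences in change matter, and the documents give no figure for those. They describe this fatigue as stabilising by 12 months and require 12 months since injury at every site. A different fatigue course at the added centres is therefore an inference from setting and recruitment route. This part of the objection stands, and it limits the size of the point.

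The absence of strata is read from silence and from the wording of a single sequence; the protocol never says that site lists are not used. If they exist, stating so settles the allocation half.

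The covariate rule in section 6.b is only a partial safeguard. Site is not plainly a demographic or clinical variable. A 15-point imbalance is 0.15 / 0.102 = 1.5 SD, which would usually not reach significance. Rehabilitation status might enter by that route, but only after looking at the data.

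Finally, four separate lists would leave incomplete blocks at small centres: 40 participants over three centres is about 13 each. That stands, and it favours two strata.

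**Conclusion.** The point holds as a cheap improvement. The documents describe one blocked sequence with no stratification factor and models with no site term, in a trial where added centres may supply 32-42% of enrolment after one year and 63-84% after two. Validity is not in question. The exposure is up to about a 15% chance of a 15-point difference between arms in site share, less if the added centres start late, and about 2-4 points of power if sites differ by 0.5 SD in change. This rests on assumed recruitment of one to two years, on 30-40 a year being the total for all three centres within the 95, and on an assumed site difference in change. If sites do not differ in change, nothing is lost on the pre-post interaction. The sample size need not change.

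**What to change.** For participants still to be randomised, generate separate blocked sequences with even block sizes for two strata, Mount Sinai and Centre for Neuro Skills, held by the same independent staff member. In sections 6.b and 6.c, pre-specify site group and site-group-by-time as fixed effects in the longitudinal models for H1-H3, in place before treatment is added and not subject to selection by fit. For the three-assessment model, give the site-group-by-time term the same form of time as the treatment-by-time term.

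The cost is new lists, some incomplete blocks, a short addition to the plan and one or two degrees of freedom. Interaction power remains about 81% if site explains nothing.
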